5.5 Analysis Plan

All statistical analyses will be based upon the total cohort of patients randomized into the trial. Although data on some patients may be missing, all relevant data available from each patient will be employed in the analyses. Patients will be included in the treatment group to which they were randomly assigned regardless of compliance.

The primary analysis will consist of a simple comparison of binomial proportions. The relative risk and confidence interval will be reported. If the treatment groups are found to differ on a pre-treatment factor

known to be a risk factor for the outcome, the statistical analysis will adjust for these differences. An evaluation of treatment by center interaction will be included. An analysis adjusting by center also will be performed to ensure that center differences do not change the conclusion.

Loss to follow-up will be defined as no information regarding transfusion or maternal survival through seven days postpartum, or maternal discharge if sooner. Those defined as lost to follow-up will not be included in the primary analysis. It is expected that the loss to follow-up rate will be negligible.

Since many of the secondary endpoints are dichotomous variables like the primary outcome, standard statistical methods for rates and proportions will be appropriate. The Wilcoxon rank sum test will be used to compare continuous variables, and survival analysis methodology may be used to compare time-to-event variables.

In general, analyses of data will be conducted to address the primary and secondary research questions of the trial, and other interrelationships among elements of study data of interest to the investigators and of relevance to the objectives of the study.

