- 21. No hemoglobin result available from the last 4 weeks, since it is necessary to measure the postoperative change in hemoglobin
- 22. Scheduled cesarean delivery and quota for scheduled deliveries already met. Quotas on the number of scheduled and unscheduled deliveries will be placed to ensure approximately equal distribution of scheduled and unscheduled cesarean deliveries.
- 23. Participating in another intervention study where the primary outcome includes postpartum bleeding or thromboembolism, or the study intervention directly affects postpartum bleeding or thromboembolism.
- 24. Participation in this trial in a previous pregnancy. Patients who were screened in a previous pregnancy, but not randomized, may be included.

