4.3 Baseline Procedures

In addition to information collected for eligibility, the following information will be obtained at randomization from a patient interview followed by a review of her chart:

- Demographic information: age, race, insurance status
- Medical history: pre-pregnancy weight, current weight, height, chronic disease history
- Obstetrical history including outcome of all prior pregnancies and history of vaginal bleeding in the current pregnancy
- Pre-randomization maternal and labor information

If not already done in the prior 4 weeks, hemoglobin and hematocrit levels will be obtained and recorded preoperatively.

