- 16. Change in hemoglobin from before cesarean to lowest measured in first 48 hours postpartum
- 17. Maternal TXA-related side-effects (nausea, vomiting, dizziness)
- 18. Open label use of TXA or other antifibrinolytic
- 19. Length of stay after delivery
- 20. Re-admission within 6 weeks postpartum
- 21. Any transfusion-associated reactions within 7 days postpartum.

Central blinded chart reviews will be conducted by the protocol subcommittee to confirm the accuracy of the following diagnoses: transfusion related acute lung injury (TRALI), thromboembolic events, ischemic stroke, myocardial infarction, and new-onset seizure activity.

5 Statistical Considerations

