5.4 Interim Analysis

The DSMC meets in person at least once per year and more often if recommended by the committee. For this trial, the DSMC will conduct a six-monthly regular safety review of cumulative adverse events.

Before each of the annual meetings, a formal detailed report will be written by the Biostatistical Coordinating Center (BCC) which presents all baseline variables, protocol adherence, side effects, all adverse events reported, as well as center performance in terms of recruitment, data quality, loss to follow-up and protocol violations.

Once a sufficient number of patients have been accrued into the trial, the report will also include a formal interim analysis evaluating the primary outcome by treatment group. For this evaluation, a cohort of patients is chosen consisting of all patients randomized before a certain date so that the analysis cohort is unaffected by delayed outcome reports.

The main statistical issue relevant to interim analysis is the problem of performing multiple tests of significance on accumulating data. For this trial, the group sequential method of Lan and DeMets will be used to characterize the rate at which the type I error is spent.³⁶ This method is flexible with regard to the timing of the interim analyses.

Asymmetric stopping boundaries will be used for the Lan-DeMets procedure. The upper boundary which describes the stopping rule for benefit will be based on 1-sided type I error of 0.025 and the Lan-DeMets generalization of the O'Brien-Fleming boundary. The lower boundary will be based on a less stringent stopping rule: 1-sided type I error of 0.05 and the Lan-DeMets generalization of the Pocock-type boundary. If the primary outcome is significant or the trial is stopped early for benefit, the methods of Maurer and Bretz will be used to test formally the major secondary endpoint of estimated blood loss while controlling the familywise error rate.³⁷

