5.5.1 Subgroup Analyses

If the two groups show a difference in the incidence of the primary outcome, interactions will be evaluated and subgroup analyses conducted to determine whether the effect prevails throughout particular subgroups of patients. Indeed, NIH guidelines require investigators to evaluate consistency between the genders and across racial subgroups. It should be noted, however, that subgroup analyses have been greatly abused, particularly when there is no overall treatment difference. There is a strong temptation to search for a specific subpopulation in which the therapy is nevertheless effective. Yusuf et al. concluded "the overall 'average' result of a randomized clinical trial is usually a more reliable estimate of the treatment effect in the various subgroups examined than are the observed effects in individual subgroups." Thus subgroup analyses will be interpreted with care.

It is generally acknowledged that subgroup analysis that is pre-specified in the protocol has more validity than ad-hoc comparisons. The following factors will be considered for subgroup analysis, if there is a significant interaction between the factor of interest and the treatment effect.

- Race/ethnicity
- Category of cesarean delivery (scheduled and unscheduled)
- Category of cesarean delivery (primary and repeat)
- Body mass index (BMI) at delivery (obese versus non-obese)
- Gestational age at randomization (< 34, 34-36,and ≥ 37 weeks)
- Preoperative hemoglobin level
- Number of fetuses (singleton and twin)
- Length of labor (within unscheduled cesareans only).

6 Data Collection

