Appendix A Design Summary

OBJECTIVE: To determine whether intraoperative tranexamic acid reduces the need for red blood cell transfusion in women undergoing cesarean delivery.

ORGANIZATION		SCHEDULED EVALUATIONS	/ DATA COLLECTION
Clinical Centers:	Magee, UAB, Ohio State, Utah, Brown, Columbia, Case Western, UT-Houston, UNC, Northwestern, UTMB-Galveston, U Penn	Pre-randomization:	 Hemoglobin and hematocrit Pregnancy, exposure and medical history Gestational age
Subcommittee: DESIGN	[name] (Chair)	Post-randomization:	 Delivery and post-operative data Hemoglobin and hematocrit 0-48 hours post-delivery Phone call to assess readmissions and treatments at 1-2 weeks postpartum Phone call to assess complications and treatments at 6 weeks postpartum
Major Eligibility Criteria:	Cesarean deliverySingleton or twin gestation	MANAGEMENT PROTOCOL	
Groups:	Tranexamic acid (TXA)Placebo	Both Groups:	 Study medication infused immediately after cord clamping, and run over 10 minutes
Random Allocation:	 Simple randomization; 1:1 allocation 	OUTCOME	
Level of Masking:	 Double-masked 	Primary:	 Transfusion of packed RBCs or maternal death
Stratification:	 Clinical site 	Secondary:	 Composite of treatments for blood loss
Sample Size:	❖ 11,000	,	 Estimated blood loss Transfusion of other blood products
Assumptions:	 Outcome event=transfusion of packed RBCs or maternal death Placebo group event rate = 2.5% TXA group event rate = 1.67% (33% reduction) Type I error = 5% (two sided) Power = 85% 		 Transfusion of other blood products Transfusion-related morbidities Thromboembolic events Change in hemoglobin from baseline
		TIMETABLE	
Interim Analysis:	 Lan-DeMets group sequential method 	Enrollment: Data Collection: Closeout/Analysis	 November 2017 to October 2020 November 2017 to December 2020 January 2021 to August 2021

References

- 1. Organization WH. The World Health Report, 2005: Make Every Mother and Child Count. Geneva: World Health Organization; 2005.

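### Change in hemoglobin (secondary outcome 16) is compared by a rank-sum test on raw change; a baseline-adjusted rank test would usually be a little more precise, at almost no cost

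*Combined protocol and SAP*

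**What the plan says.** Section 4.6.3 defines item 16 as "Change in hemoglobin from before cesarean to lowest measured in first 48 hours postpartum". Appendix A lists it among the secondary outcomes as "Change in hemoglobin from baseline".

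Section 5.5 gives one general rule for such outcomes, "The Wilcoxon rank sum test will be used to compare continuous variables", and names no covariate. That the test is run on raw change is inferred by reading this rule with the endpoint definition; the plan does not say it outright.

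The preoperative value is secured by design. Section 3.4.2, item 21, excludes a woman with "No hemoglobin result available from the last 4 weeks, since it is necessary to measure the postoperative change in hemoglobin", and Section 4.3 adds: "If not already done in the prior 4 weeks, hemoglobin and hematocrit levels will be obtained and recorded preoperatively".

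Preoperative hemoglobin appears in the analysis plan in only one other role, as a subgroup factor in Section 5.5.1 ("Preoperative hemoglobin level"). The covariate-adjustment clause in Section 5.5 is conditional ("If the treatment groups are found to differ on a pre-treatment factor") and sits in the paragraph on the primary analysis.

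**The concern.** The trial requires a baseline hemoglobin from everyone, and the planned test uses it in only one way, by subtraction. Subtraction is the best linear use of a baseline only when the regression slope of the postoperative on the preoperative value is 1. At any other slope, some baseline variation stays in the change score as noise, and a comparison that estimates the slope removes it.

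What is at stake is precision on one secondary outcome. It deserves some care because it is a laboratory measure of bleeding, whereas blood loss is estimated visually (Section 4.4). Section 5.5 also names an effect measure for the primary outcome (relative risk with confidence interval) but none for continuous outcomes.

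**Working it through.** **Inputs from the documents.** 11,000 women allocated 1:1, so 5,500 per arm; two-sided alpha 0.05 (Sections 3.6 and 5.2). A postoperative value is not guaranteed for every woman, so 5,500 per arm is a ceiling for this outcome.

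**Assumed, because the documents give nothing.** Pre-post correlation ρ = 0.4 to 0.8; post/pre SD ratio k = 1 to 1.25; residuals normal, t(5), or left-skewed lognormal (sigma 0.5).

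**Step 1: the plan's nearest figure.** There is no power statement for hemoglobin. The only Wilcoxon calculation is for blood loss in Section 5.2: a 25 cc difference with SD 300. P = Φ(−25/(300√2)) = Φ(−0.0589) = 0.4765, which agrees with the stated 0.477. Noether's formula gives power Φ(√(12 × 0.25 × 11,000) × 0.0235 − 1.96) = 0.99, so the plan's description of that power as ample is right.

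**Step 2: relative efficiency.** Measure hemoglobin in preoperative SDs. Let post = b·pre + residual + treatment shift, with b = kρ and residual SD k√(1−ρ²). Then change = residual + (b−1)·pre + shift. The planned test carries the extra term (b−1)·pre; the adjusted test does not.

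With normal residuals, the efficiency of planned relative to adjusted is

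k²(1−ρ²) / (1 + k² − 2ρk).

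The denominator exceeds the numerator by (1−ρk)², so the ratio never exceeds 1 and equals 1 when ρk = 1. At k = 1 it reduces to (1+ρ)/2. For other shapes the ratio is (∫f²_change / ∫f²_residual)². If the residual is independent of baseline, adding the extra term cannot raise ∫f², so this ratio is also at most 1.

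| Residuals | k = 1; ρ 0.4 / 0.6 / 0.8 | k = 1.1 | k = 1.25 |
|---|---|---|---|
| Normal | 0.70 / 0.80 / 0.90 | 0.76 / 0.87 / 0.97 | 0.84 / 0.94 / 1.00 |
| t(5) | 0.61 / 0.73 / 0.85 | 0.69 / 0.82 / 0.95 | 0.78 / 0.91 / 1.00 |
| Skewed | 0.52 / 0.64 / 0.79 | 0.60 / 0.74 / 0.92 | 0.70 / 0.87 / 1.00 |

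**Step 3: what this means at 5,500 per arm.** The shift detectable with 80% power is 2.8016 × √(2/5500) × SD / (√12 ∫f²). For normal data √12 ∫f² = √(3/π) = 0.977, so the shift is 0.0547 × SD. At k = 1 the SD of change is √(2(1−ρ)) and the residual SD is √(1−ρ²).

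| ρ | Planned | Adjusted | Fall (preoperative SD) |
|---|---|---|---|
| 0.4 | 0.0547 × 1.095 = 0.060 | 0.0547 × 0.917 = 0.050 | 0.010 |
| 0.6 | 0.0547 × 0.894 = 0.049 | 0.0547 × 0.800 = 0.044 | 0.005 |
| 0.8 | 0.0547 × 0.632 = 0.035 | 0.0547 × 0.600 = 0.033 | 0.002 |

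The largest fall in the step 2 grid is 0.015 SD (0.054 to 0.039; skewed, ρ = 0.4, k = 1).

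In g/dL, with an assumed SD of 1.2 and k = 1, simulated power for a 0.05 g/dL difference rises from 58% to 70% at ρ = 0.5, from 79% to 86% at 0.7 and from 92% to 94% at 0.8. For 0.10 g/dL both tests have at least 99% power.

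**Step 4: departures from the model.** If skewed residual spread falls with baseline (ρ = 0.4, equal SDs), the ratio is 0.46 and the detectable shift falls from about 0.056 to 0.038, or 0.018 SD. If skewed residual spread rises with baseline (slope 0.8), the ratio is 1.026 or 1.048, depending on how the spread is scaled. Adjustment then loses about 2 to 5%. That figure belongs to this scenario and is not a bound.

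**Step 5: type I error.** In simulations of 27 scenarios, the rejection rate under no effect averaged 5.2% for the planned test and 5.0% for the adjusted test (Monte Carlo SE 0.7 points per scenario). Both are valid.

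**The case against.** The case against is that this is a preference and not a defect. A rank test on change is standard, already uses the baseline, and follows one uniform rule for continuous outcomes. No sample size or power statement rests on item 16, which is one of 21 secondary outcomes. The only secondary endpoint in the controlled sequence is blood loss; Section 5.4 plans to "test formally the major secondary endpoint of estimated blood loss while controlling the familywise error rate". The gain depends wholly on assumed values and disappears at slope 1. Nothing in Section 5.5 forbids a supportive adjusted analysis. All of this stands, and it sets the severity. It does not remove the point: the data are already required, the conditional adjustment clause and the subgroup listing do not supply routine adjustment, and the change is a matter of wording.

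A second objection is that the remedy pairs a rank p-value with a linear-model interval, and the two can disagree. That also stands, so the plan should say which governs.

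A reader might infer that the planned analysis is biased or ignores baseline. It does neither. Randomization makes the comparison of change valid, and change subtracts the baseline. A reader might also infer that ordinary linear ANCOVA should replace the test. The calculations do not support that: the planned test was more efficient than linear ANCOVA in 12 of 18 non-normal scenarios, by a ratio of up to 1.58.

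**Conclusion.** The point holds as an optional, nearly free improvement. Raw change usually costs a little precision because it fixes the slope at 1. With normal residuals the planned test's relative efficiency is 0.70 to 1.00 over the assumed range, and skewed or heavy-tailed residuals can take it lower. At this sample size the practical difference is small: 0.002 to 0.010 preoperative SD in detectable shift with normal residuals and equal SDs, and at most about 0.018 SD in the scenarios computed. A small loss is possible if skewed residual spread rises with baseline. Every figure rests on assumed correlations, SD ratios and residual shapes, so the gain in this trial is unknown. No formally controlled conclusion depends on this outcome.

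**What to change.** In Section 5.5, pre-specify for secondary outcome 16:

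- **Test.** Regress the lowest 48-hour hemoglobin on preoperative hemoglobin by linear regression, with both arms pooled and no treatment term, and compare the residuals between arms by a Wilcoxon rank sum test. The residuals do not use treatment labels, so the test stays valid under no treatment effect even if the linear fit is wrong.
- **Estimate.** Report the baseline-adjusted mean difference in g/dL with a 95% CI, from a linear model with treatment and preoperative hemoglobin.
- **Precedence.** State that the rank test supplies the p-value, and that the CI is descriptive and may occasionally disagree with it.

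The blood-loss analysis is unchanged. The cost is a few sentences of plan wording and no new data. The trade-off is that ranked residuals are harder to explain than ranked change; the g/dL estimate helps with that.

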5.5.1 Subgroup Analyses

If the two groups show a difference in the incidence of the primary outcome, interactions will be evaluated and subgroup analyses conducted to determine whether the effect prevails throughout particular subgroups of patients. Indeed, NIH guidelines require investigators to evaluate consistency between the genders and across racial subgroups. It should be noted, however, that subgroup analyses have been greatly abused, particularly when there is no overall treatment difference. There is a strong temptation to search for a specific subpopulation in which the therapy is nevertheless effective. Yusuf et al. concluded "the overall 'average' result of a randomized clinical trial is usually a more reliable estimate of the treatment effect in the various subgroups examined than are the observed effects in individual subgroups." Thus subgroup analyses will be interpreted with care.

It is generally acknowledged that subgroup analysis that is pre-specified in the protocol has more validity than ad-hoc comparisons. The following factors will be considered for subgroup analysis, if there is a significant interaction between the factor of interest and the treatment effect.

- Race/ethnicity
- Category of cesarean delivery (scheduled and unscheduled)
- Category of cesarean delivery (primary and repeat)
- Body mass index (BMI) at delivery (obese versus non-obese)
- Gestational age at randomization (< 34, 34-36,and ≥ 37 weeks)
- Preoperative hemoglobin level
- Number of fetuses (singleton and twin)
- Length of labor (within unscheduled cesareans only).

6 Data Collection

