5.2 Sample Size and Power

The table below provides the sample size calculations needed to achieve 80-90% power to detect 30-40% difference in the primary outcome between women receiving TXA or placebo at time of their cesarean, using a two-tailed alpha of 0.05. The Poisson approximation to the normal distribution was used in the estimation of the sample sizes.

Table 1. Total Sample Sizes for TXA vs. Placebo for Various Primary Outcome Rates

Risk reduction	Power (%)	Primary Outcome Rate in Placebo Group			
(%)	(70)	1.5%	2.5%	3.5%	
30	80	19,800	11,900	8,500	
	85	22,700	13,600	9,700	
	90	26,500	15,900	11,400	
33.3	80	15,700	9,500	6,800	
	85	18,000	11,000	7,700	
	90	21,100	12,700	9,000	
35	80	14,100	8,500	6,100	
	85	16,200	9,700	7,000	
	90	18,900	11,400	8,100	
40	80	10,500	6,300	4,500	
	85	12,000	7,200	5,200	
	90	14,000	8,500	6,000	

Since quotas will be issued to ensure approximately equal enrollment between scheduled and unscheduled cesareans, a sample size of 11,000 women (5,500 in the scheduled and 5,500 unscheduled) will achieve 85% power to detect a 33% reduction in primary outcome overall, assuming that the placebo rate is 2.5%.

The power to detect an interaction between treatment effect and scheduled versus unscheduled cesarean delivery (see Section 5.5.1) was estimated under the following assumptions: 1.5% outcome rate in the placebo group in the scheduled cesarean deliveries, 3.5% primary outcome rate in the placebo group in the unscheduled cesarean deliveries, no overall reduction in the primary outcome. With a sample size of 11,000, there is more than 85% power to detect an odds ratio for 3 for the interaction in a logistic regression and more than 75% if the odds ratio is 2.5.35

If there is a significant interaction between treatment effect and scheduled versus unscheduled cesarean delivery (Section 5.5.1) the effect of treatment within each group will be presented separately. There is more than 85% power to detect a 40% reduction in the primary outcome within the unscheduled cesarean deliveries and more than 75% power to detect a 50% reduction within the scheduled cesarean group.

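### Subgroup effects are to be examined only for factors that pass an interaction test of unstated level, a filter that selects exaggerated contrasts and cannot display consistency

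*Combined protocol and SAP*

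**What the plan says.** Section 5.5.1 sets two conditions in sequence. The first concerns the overall result: "If the two groups show a difference in the incidence of the primary outcome, interactions will be evaluated and subgroup analyses conducted". The second concerns each factor: "The following factors will be considered for subgroup analysis, if there is a significant interaction between the factor of interest and the treatment effect". Eight factors follow: race/ethnicity, scheduled or unscheduled cesarean, primary or repeat cesarean, obesity, gestational age, preoperative hemoglobin, number of fetuses and, among unscheduled cesareans, length of labor.

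Section 5.2 repeats the second condition for scheduled versus unscheduled. If that interaction is significant, "the effect of treatment within each group will be presented separately". This is the only listed interaction with stated power: more than 85% for an interaction odds ratio of 3 and more than 75% for 2.5, computed on the assumption of no overall reduction.

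No significance level or multiplicity rule for the interaction tests appears anywhere. Section 5.4, by contrast, does control the familywise error for the major secondary outcome. Section 5.5.1 also notes that "NIH guidelines require investigators to evaluate consistency between the genders and across racial subgroups", and it closes its general discussion with "Thus subgroup analyses will be interpreted with care".

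**The concern.** The purpose given in Section 5.5.1 is to learn whether the effect holds across subgroups. A rule that opens a factor for subgroup analysis only after homogeneity has been rejected cannot show that. It also selects on extremeness, so the subgroup estimates that appear are those pushed furthest from the common effect. This pulls against the principle the section itself quotes, that the overall result is usually the better guide to the effect in a subgroup.

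The practical risk is that a uniform benefit is presented as strong in one kind of patient and weak or absent in another, and prophylaxis is then targeted or withheld on a chance finding. Race/ethnicity sits behind the same filter, although the section cites a requirement to look at consistency by race.

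**Working it through.** **Inputs from the documents.** 11,000 women, 1:1 allocation, half scheduled and half unscheduled; placebo rate 2.5% overall (1.5% scheduled, 3.5% unscheduled); 33% reduction; two-sided 0.05 for the primary outcome; eight factors. **Assumptions.** 5% per interaction test; no true interaction unless stated; an overall difference means a two-sided p-value below 0.05.

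**1. The plan's own figure.** Section 5.2 says that 11,000 women "will achieve 85% power to detect a 33% reduction in primary outcome overall, assuming that the placebo rate is 2.5" percent. With Poisson variances, N = 2(1.960 + 1.036)² (p1 + p2)/(p1 − p2)². For p1 = 0.025 and p2 = 0.01667 this gives 17.96 × 600 ≈ 10,774; for p2 = 0.01675 it gives about 11,015. The normal-approximation power at 5,500 per arm is 0.857 to 0.864. The stated 85% is reproduced, and it is also roughly the chance that the first condition of Section 5.5.1 is met under the design effect.

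**2. Any false-positive factor, given an overall difference.**
- Eight independent 5% tests: 1 − 0.95⁸ = 33.7%.
- Equally correlated tests: 32% at correlation 0.2, 25% at 0.5, 16% at 0.8.
- Two simulations of 11,000 women with a relative risk of 0.667 in every subgroup and differing assumed factor prevalences: 29% and 30%. Tests in small strata are conservative.
- The level matters: 1 − 0.99⁸ = 7.7% at 1%, and 1 − 0.90⁸ = 57% at 10%.

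**3. Per trial, counting the first condition.**
- Design effect: 0.864 × 0.337 = 29%; 25% in the simulation that tracked both conditions.
- No treatment effect: 0.05 × 0.337 = 1.7%.
- No treatment effect, with scheduled versus unscheduled tested regardless: 0.05 + 0.95 × 0.05 × (1 − 0.95⁷) = 6.4%.

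**4. Size of a contrast that passes.** Take scheduled versus unscheduled with a uniform relative risk of 0.667 and 2,750 women per cell.
- Expected events: 41.25 and 27.5 (scheduled, placebo and TXA); 96.25 and 64.17 (unscheduled).
- Variance of the log ratio of odds ratios: 1/41.25 + 1/27.5 + 1/96.25 + 1/64.17 = 0.0866, plus 0.0015 for non-events, giving 0.0881. SE = 0.297.
- Smallest significant contrast: exp(1.96 × 0.297) = 1.79-fold.
- Median significant contrast with no true interaction: about 1.95-fold by simulation. With a true 1.5-fold interaction (power 28%) it is about 2.07-fold.

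For scale, hold the pooled odds ratio at 0.66 and split ln 1.95 = 0.668 between the strata in proportion to their variances (0.0613 scheduled, 0.0267 unscheduled; shares 0.70 and 0.30). The odds ratios shown would be about 0.66 × exp(0.465) = 1.05 scheduled and 0.66 × exp(−0.203) = 0.54 unscheduled. In the other direction they would be about 0.41 and 0.81. The true effect is the same in both strata.

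**5. Race/ethnicity.** With a consistent effect the interaction passes about 5% of the time, so race-specific estimates are unshown in about 95% of trials. The simulation gave 95.6%, or 96.1% once the first condition was counted.

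**6. The two sections side by side.** Section 5.2 computes the scheduled/unscheduled interaction power assuming no overall reduction. That is a setting in which Section 5.5.1 does not provide for interactions to be evaluated.

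**The case against.** The strongest reply is that the plan is already cautious. The factors are listed in advance, a subgroup needs an interaction test and not merely a within-subgroup p-value, and an overall difference is required first. That requirement blocks the search for a responsive subgroup in a null trial, and it works: the per-trial false-positive rate is then about 2-6%. These analyses are secondary, and the primary result is untouched. All of this stands.

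Three stronger readings are tempting but not supported.
- A reader might infer that about one trial in three would publish a spurious subgroup. The 33.7% applies only once there is an overall difference, and it assumes eight independent tests at a level the plan does not give. The plan also speaks of factors being considered for analysis, not of publication.
- A reader might infer that the requirement on racial consistency is defeated. The interaction test is itself some evaluation of consistency; what is not assured is the race-specific estimates.
- A reader might infer that non-significant interaction results will be withheld. No passage says so.

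It is also fair to say that full reporting would still display the same chance contrasts. It would display them among all eight factors, however, so that no contrast is picked out by its p-value.

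The caution does not answer the selection problem. Interpreting with care sets no operating rule. A non-significant interaction test of unstated power does not establish consistency, whereas estimates with confidence intervals show what the data can exclude.

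**Conclusion.** The point holds as a defect in how subgroup results are selected. Given an overall difference and no true interaction, the chance of at least one false-positive factor is up to about 30-34%; per trial it is about 25-29% under the design effect and about 2-6% with no treatment effect. Scheduled versus unscheduled must reach about 1.8-fold to pass, with a median of about 1.95-fold by chance alone. Race-specific estimates would be unshown in about 95% of trials with a consistent effect.

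The error rates rest on a 5% level that the plan does not state. The simulated figures also rest on factor prevalences that are not in the documents, and strong correlation among the tests would lower the conditional rate to 16-25%. The exaggeration for scheduled versus unscheduled needs only the plan's own rates and sample size and the assumed 5% level. The mismatch between Sections 5.2 and 5.5.1 on the overall-difference condition needs no assumption about factor prevalences and should be reconciled.

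**What to change.** - In Sections 5.5.1 and 5.2, replace the significance filter with a commitment to report the relative risk and 95% CI at every level of all eight prespecified factors, with each interaction p-value, whatever that p-value is.
- Name scheduled versus unscheduled, the only listed interaction with stated power, as the one interaction formally tested at 5%. Label the other seven as descriptive. No further multiplicity correction is then needed.
- State whether the scheduled/unscheduled test requires an overall difference first, so that Section 5.5.1 agrees with the power calculation in Section 5.2.

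The cost is a wording change and one larger table, with no new data and no change to the primary analysis. The downside is that the other seven factors can no longer support stand-alone significance claims, for which no power is stated in any case.
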